C5. Randomization. **a. Primary Tailoring Variable (PTV):** The PTV determines the set of randomized intervention options. Thus, the PTV in any SMART must be a proximal measure of the outcome that denotes early success or failure and can be implemented in practice²⁸. In this SMART, the PTV is a predetermined benchmark for adequate implementation. This benchmark will be based on C-SSRS Screener fallouts and CSRE fallouts. The cut-off for both must be 80% or higher (i.e., less than 20% fallouts) to be considered adequate implementation. This cut-off was chosen with input from the program partner and previous QI projects with the program office that involved setting implementation benchmarks (i.e., REACH VET implementation). This benchmark is meant to represent a performance target that all facilities are expected to work towards. Preliminary data indicates that, across facilities since October 2018, the 1st quartile of C-SSRS fallouts is 47.9% (range: 12.9% - 87.4%), and the 1st quartile of the CSRE fallouts is 61.2% (range: 12.5% - 100%). 75% of sites currently have C-SSRS and CSRE fallout percentages greater than 47.9% and 61.2%, respectively. Based on these numbers at least 80-90% of sites currently do not meet criteria for adequate performance. We expect that this number to decrease some as implementation continues, but we expect that many sites will still have significant room for improvement when this project begins. The program partner may adjust this benchmark based on additional data gathered. **b.** Randomization procedures: Randomization will occur at the site level. VAMCs that are not meeting the benchmark for adequate implementation (See PVT above) at Baseline month 6 will be randomized 1:1 (R1) to receive A/F or continued IAU for 10 months. A/F sites that do not meet the benchmark for adequate implementation at the 10th interventional month will be randomized 1:1 (**R2**) to either continue A/F or augmentation with EF (A/F + EF) for an additional 10 months. A/F sites that meet the criteria for adequate implementation will be randomized 1:1 (**R3**) to either continue A/F or discontinue A/F and return to IAU. R1 will be stratified by facility complexity level (i.e., high, medium and low) and level of performance (i.e., low or moderate) at baseline. The Facility Complexity Model²⁹ classifies VA medical facilities at levels 1a, 1b, 1c, 2, or 3. Level-1a facilities are the most complex and level-3 facilities are the least complex. Levels 1a-1c will be considered high complexity, level 2- medium complexity and level 3- low complexity. Approximately 61% of facilities (N=85) are high complexity, 17% (N=24) are moderate and 22% (N=31) are low complexity. Additionally, the average of the C-SSRS Screener and CSRE fallout rates for the 6th Baseline month will be calculated for each facility to be randomized (R1) and the median of these averages will be used to determine stratification by level of performance (i.e., low – above median fallout rate, or moderate – below median fallout rate). R2 will also be stratified by facility complexity level and level of performance (based on the median of the fallout rate at the 10th month of phase 1). R3 will be stratified only by facility complexity level as all sites will have met the benchmark. These procedures will ensure that intervention groups are balanced for site variables that may correlate highly with outcomes. If less than 12 sites will be randomized at R2, stratification will only occur based on facility complexity, unless all facilities are at the same level of complexity in which case only median level of performance will be used for stratification.

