EPRP outcomes of change in sui2 and csra1 from the 6th month of the baseline period to the 10th month of the first interventional phase will each be modeled as a function of group (A/F vs. IAU), the baseline outcome value, the stratification variables of facility complexity (high, medium, low) and baseline performance level (above or below the median average fallout rate), and geographic region (West, Midwest, Southwest, Southeast and Northeast). Inference will be made based on the coefficient associated with the group variable and 97.5% confidence intervals (CI) will be reported (alpha=0.025). A similar analysis will be used to determine the effect of A/F on the change in the EPRP outcome for the primary screeners (sui40 and sui51), with 95% CIs reported. **c.** Secondary Aims: 1). To test the effect of the addition of EF for those who do not implement adequately at end of interventional phase 1, the primary EPRP outcomes of change in sui2 and csra1 from the 10th month of interventional phase 1 (baseline for interventional phase 2) to the 10th month of interventional phase 2 will be modeled as a function of group, the baseline outcome value, the stratification variables and geographic region (if sample sizes allow for control of this variable). Inference will be made based on the coefficient associated with the group variable and 95% CIs will be reported. A similar analysis will be used to determine the effect of the addition of EF on the change in the EPRP outcome for the primary screeners (sui40, sui51), with 95% CIs reported. 2). An analysis similar to that described for secondary aim 1 will be employed to investigate the effect of discontinuing A/F for those who implemented adequately at the end of interventional phase 1. Lastly, we will use a data driven approach to characterize each of the four EPRP outcomes over time for each group outlined in Figure 2 (group 1-6). Mixed effects models with a random intercept and slope will be used to model each of the four EPRP outcomes as a function of categorical group (1-6) and an interaction between group and a Bspline transformation on time (allowing the outcome to vary smoothly over time, using 21-time points, i.e., the 6th baseline month and every month of each interventional phase) such that each group will have its own trajectory. The trajectory for each group will be plotted with pointwise confidence intervals. **d. Exploratory** Aims: *i. Reach*: Reach will be calculated using the following formula: actual number of Veterans screened or evaluated/ actual number of Veterans eligible for screening, calculated cumulatively across all three study phases and all sites. We will calculate reach for each assessment stage of VA Risk ID. We will examine representativeness of patients reached by comparing demographic characteristics and other relevant variables (e.g., settings in which screening was completed) between eligible Veterans who were screened and/or evaluated and those who were not. Given that Veterans are clustered within facility, if the intra-class correlation between Veterans within each facility is estimated to be greater than zero, methods appropriate for clustered data will be employed to compare the variables of interest. For continuous variables, linear mixed models will be used with a random facility effect and non-normal data will be transformed. For binary variables, generalized linear mixed models will be used with a logit link and for categorical variables, random effects multinomial models will be employed. If the ICC is zero, t-tests, Wilcoxon rank-sum, Chi-square or Fisher's exact tests will be used, as appropriate. *ii. Adoption & Implementation Factors:* Key informant interviews will be used to examine factors influencing adoption of the implementation interventions and barriers and facilitators of implementing VA Risk ID to fidelity. All qualitative data sources, including interview transcripts and documents will be compiled and managed using Nvivo V. 9.0 software. We will take a general inductive approach³⁴. Specifically, data analysis will be determined by both the research objectives (i.e., domains of the RE-AIM framework) and multiple readings and interpretation of the raw data (i.e., content analysis). The goal is to establish clear links between the research objectives and the summary findings derived from the raw data. *iii. Effectiveness- Clinical Innovation:* We wish to examine whether Veterans who receive the CSRE are more likely to receive a safety plan within 2 weeks than those who screen positive on the primary screen only. To account for clustering of Veterans within facility, a mixed-effects logistic regression will be used to model the outcome of safety plan within 2 weeks (yes/no) as a function of group (receipt of CSRE/positive on primary screen only) with a random subject within facility effect. Additionally, to determine if receipt of a timely safety plan depends on whether Veterans are considered to be at low, moderate or high acute risk of suicide, this model will be repeated with the addition of a group by (categorical) acute risk interaction. Odds ratios for receipt of CSRE relative to positive on primary screen only will be reported for each level of acute risk with 95% confidence intervals.

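### Exploratory Aim 3 is meant to allow for Veterans clustered in facilities, but the only random effect it names is for the subject; a facility intercept should be stated

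*Protocol*

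**What the plan says.** Protocol C7, d. Exploratory Aims, iii compares Veterans who received the CSRE with those positive on the primary screen only; the outcome is a safety plan within two weeks. The purpose of the model is plain: "To account for clustering of Veterans within facility, a mixed-effects logistic regression will be used". The specification that follows models the outcome "as a function of group (receipt of CSRE/positive on primary screen only) with a random subject within facility effect". No other random effect is named.

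For acute risk, "this model will be repeated with the addition of a group by (categorical) acute risk interaction", and the odds ratios "will be reported for each level of acute risk with 95% confidence intervals". The second model therefore takes over the random-effects structure of the first.

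Two other places name the cluster directly. The Reach analysis in the same section puts a random effect on facility in its linear mixed models for continuous variables. The SAP's primary-aim model has a random intercept that it identifies as a site effect. The SAP covers the primary and secondary aims only, so C7 is the sole specification of Exploratory Aim 3.

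**The concern.** The purpose and the named term do not match. A random effect for subject nested in facility makes records from the same Veteran alike. It leaves two different Veterans at the same facility independent, and that is the correlation the model is said to be there for. An analyst who followed the phrase to the letter would fit a model that does not do its stated job.

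At stake are the odds ratio and CI for the one comparison that C1, Table 1 lists under effectiveness of the clinical innovation, and the risk-specific odds ratios from the interaction model. No primary or secondary result depends on it.

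**Working it through.** The documents give no ICC, event rate, number of Veterans per facility or odds ratio for this aim, so there is no planned figure to reproduce. Two checks show what a literal fit would do.

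**1. Can the subject variance be estimated?** Assume one binary record per Veteran and observed proportions of 0.30 (primary screen only) and 0.4615 (CSRE). For a subject SD s, find the linear predictors e0 and e1 whose logistic probabilities, averaged over a normal effect with SD s, equal those proportions. The conditional odds ratio is exp(e1 − e0).

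| s | e0 | e1 | Conditional OR |
|---|---|---|---|
| 0 | −0.847 | −0.154 | 2.00 |
| 1 | −1.018 | −0.186 | 2.30 |
| 2 | −1.384 | −0.254 | 3.10 |

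All three fit the data equally well. The data cannot choose s, so the reported odds ratio would depend on where the software stopped. With repeat records per Veteran s can be estimated, but correlation between Veterans at a facility is still left out.

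**2. What does leaving out facility cost?** With one record per Veteran, the literal model treats all Veterans as independent, so ordinary logistic regression stands in for it. Assumed inputs: 140 facilities (the protocol's maximum), 100 Veterans each, facility-conditional OR 2.0, intercept −0.5, 200 simulated data sets per setting. Facility variance is ICC × (π²/3)/(1 − ICC), which gives facility SDs of 0.26, 0.42, 0.60 and 0.91 at ICC 0.02, 0.05, 0.10 and 0.20. The naive SE is √(1/a + 1/b + 1/c + 1/d) from the pooled two-by-two table. The ratio is the SD of the log OR across data sets divided by the mean naive SE.

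| ICC | Ratio, CSRE receipt varies (logit SD 1) | Ratio, receipt equal |
|---|---|---|
| 0.02 | 0.0403/0.0344 = 1.17 | 0.0354/0.0344 = 1.03 |
| 0.05 | 0.0444/0.0344 = 1.29 | 0.0352/0.0344 = 1.02 |
| 0.10 | 0.0530/0.0344 = 1.54 | 0.0364/0.0343 = 1.06 |
| 0.20 | 0.0646/0.0343 = 1.88 | 0.0343/0.0343 = 1.00 |

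For an estimate centred on the null, a nominal 5% test rejects with probability 2[1 − Φ(1.96/ratio)]. In the varying-receipt column that is about 9%, 13%, 20% and 30%.

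With receipt varying, the pooled OR averages 1.98, 1.95, 1.90 and 1.81 against the facility-conditional 2.00. That shift is the usual gap between a population-averaged and a facility-conditional odds ratio. It changes what is estimated and is not confounding.

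With a random facility intercept fitted by maximum likelihood to the same data, the OR averages 1.99 to 2.01 and 95% CI coverage is 0.93 to 0.96 in all eight settings.

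**The case against.** The strongest reply is that this is loose wording. The sentence opens by naming facility clustering as the reason for the model, the section elsewhere recognises correlation among Veterans in a facility, and the phrase can be shorthand for Veterans nested in facilities with facility as the cluster. On that reading the facility effect is in the model and none of the harm above arises. This stands as a plausible reading. It does not settle the matter, because the stated intention does not define the term and no later text does.

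A subject term may also be legitimate. C4 defines the cohort by annual depression and as-required PTSD screening, and the planned phases total 6 + 10 + 10 = 26 months, so repeat episodes are possible. The protocol does not say whether each Veteran contributes one record. This stands too; it makes a Veteran term a possible addition to the facility term, but not a replacement for it.

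The sizes are all assumed, and the error is small if the ICC is low or CSRE receipt is similar across facilities. That is correct. C5 reports CSRE fallouts from 12.5% to 100% with a first quartile of 61.2%, which suggests wide variation. But these are early roll-out figures without denominators, and the CSRE follows a positive secondary screen. They are not the spread of receipt among Veterans positive on the primary screen, which is what matters here.

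A reader might go further and infer that the odds ratio also mixes facility quality with the CSRE effect. With no true within-facility effect, a facility SD of 0.5, uptake SD of 1.0 and a correlation of 0.3 between the two, the pooled OR is about 1.13. The documents give no such correlation, and in that scenario a plain facility intercept already brings the OR to about 1.02.

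**Conclusion.** The point holds as a specification fault in an exploratory analysis. The only random effect named would not, read literally, serve the purpose stated in the same sentence, and its variance is not identifiable with one binary record per Veteran. If it were fitted that way, the true SD of the log odds ratio would be about 1.2 to 1.9 times the naive SE for ICC 0.02 to 0.20 when CSRE receipt varies by facility (logit SD 1), and about 1.0 to 1.06 times when receipt is equal. These figures rest on the assumed ICC, uptake spread and 100 Veterans per facility.

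A reader might infer that facility clustering is in fact ignored and that the odds ratio and CI are wrong. The documents do not support that: they show an ambiguous term, not a fitted model. The primary and secondary aims are unaffected.

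**What to change.** In C7, Exploratory Aims, part iii, replace the random-effect phrase with a random intercept for facility, in line with the facility effect already named for Reach. State whether each Veteran contributes one episode or several, and add a Veteran-within-facility intercept only if there are several. State that the acute-risk interaction model uses the same structure. A covariate for each facility's CSRE completion proportion is optional and not part of this correction.

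The cost is a phrase or two. C3 already lists location of care among the CDW data. If a facility intercept was always intended, no rerun is needed; otherwise two models are refitted. The downside is a possibly wider CI: in the varying-receipt simulations the SE rises by a factor of 0.0368/0.0344 = 1.07 at ICC 0.02 and 0.0410/0.0343 = 1.20 at ICC 0.20.

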Examining the Effectiveness of an Adaptive Implementation Intervention to Improve Uptake of the VA Suicide Risk Identification Strategy (PEC 19-303)

NCT04243330

October 17, 2024

QUERI RISK ID Statistical Analysis

Primary Aim. Determine if the addition of Audit and Feedback in Phase 1 (February 2021 – November 2021) significantly improved eCSSRS1 and eCSRE1 adherence. To determine the effect of Audit & Feedback on Phase 1, we compared group 6 (Implementation As Usual [IAU] in Phase 1; N=66) to Groups 2, 3, 4, and 5 combined (Audit & Feedback [AF] in Phase 1; N=67). We used all available data and modeled monthly 1) eCSSRS1 and 2) eCSRE1 adherence across the entire study period (January 2021 – March 2024) for each group (IAU and AF). We chose to estimate these trajectories using natural cubic B-spline transformations on time to allow for smoothly changing trajectories and not restrict the estimation to a parametric form (e.g., polynomials). Internal knot selection for the B-splines was based on visible change points in descriptive longitudinal plots – these were November 2021, January 2022, November 2022, and March 2023 (or months 11, 13, 23, and 27). These 4 internal knots result in 5 knot spans and 5 degrees of freedom for each group/outcome combination modeled. Each outcome was then modeled as a function of group, the B-spline transformations, and group by B-spline transformation interactions so that we could estimate a trajectory for each group. These mixed effects models included a random intercept (i.e., random site effect). Contrasts were constructed within each model and were used to estimate the change in adherence for each group from February 2021 – November 2021 and the difference in adherence change between the groups, which was our hypothesis test of interest. These estimated differences in change were reported with 95% confidence intervals (CIs). For both estimates, the difference in change was calculated as the AF group minus the IAU group.

Secondary Aim 2a. For sites that responded to AF during Phase 1, determine if switching to AF Light during Phase 2 (January 2022 – July 2023) resulted in a significant decrease in eCSSRS1 and eCSRE1 adherence. To determine the effect of switching to AF Light in Phase 2, we compared Group 2 (Continued AF; N=6) to Group 3 (Switched to AF Light; N=6). We used the same approach as was used for the Primary Aim. Monthly eCSSRS and eCSRE adherence was modeled across the entire study period as a function of group (Continued AF and Switch to AF Light), B-spline transformations on time, and group by B-spline transformation interactions, so that we could estimate a trajectory for each group. Knot selection was the same as for the Primary Aim. Contrasts were constructed within each model and were used to estimate the change in adherence for each group from January 2022 – July 2023 and the difference in adherence change between the groups, which was our hypothesis test of interest. These estimated differences in change were reported with 95% Cls. For both estimates, the difference in change was calculated as the Continued AF group minus the Switch to AF Light group.

Secondary Aim 2b. For sites that did not respond to AF during Phase 1, determine if the addition of External Facilitation (EF) during Phase 2 (January 2022 – July 2023) resulted in a significant increase in eCSSRS1 and eCSRE1 adherence. To determine the effect of the addition of EF in Phase 2, we compared Group 4 (Continued AF; N=38) to Group 5 (Added EF; N=17). We used the same approach as was used for the Primary Aim. Monthly eCSSRS and eCSRE adherence was modeled across the entire study period as a function of group (Continued AF and Added EF), B-spline transformations on time, and group by B-spline transformation interactions, so that we could estimate a trajectory for each group. Knot selection was the same as for the Primary Aim. Contrasts were constructed within each model and were used to estimate the change in adherence for each group from January 2022 – July 2023 and the difference in adherence change between the groups, which was our hypothesis test of interest. These estimated differences in change were reported with 95% CIs. For both estimates, the difference in change was calculated as the Continued AF group minus the Added EF group.

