*Adequate Implementation= completion of secondary screening and CSRE for 80% or more of eligible patients; R= Randomization

strategy) will be evaluated using a sequential multiple assignment randomized trial (SMART) design. This project will occur over three phases: Run-In Phase, Intervention Phase I and Intervention Phase II. The unit of intervention is the site and randomization will occur at the site level. **Three adaptive interventions (AIs) are embedded in the SMART design:** 1. Begin with IAU, and after six months, continue IAU if the site meets the pre-determined benchmark for adequate implementation. If the site does not meet the benchmark for adequate implementation; 2. For sites that do not meet the benchmark for adequate implementation, first intervene with A/F only for 10 months. Then, if the site continues to not meet benchmark for adequate implementation: a) continue A/F alone for another 10 months or b) augment A/F by initiating a combination strategy of A/F +

external facilitation (A/F + EF) for 10 months; 3. For sites that meet the benchmark for adequate implementation after the first stage intervention (i.e., A/F for 10 months): a) continue providing A/F or b) discontinue A/F and go back to IAU for another 10 months. Up to 140 VHA facilities will be included in this QI project. Facilities will be designated into 1 of 6 groups based on performance and randomization, which will dictate how they move through the study phases and the sequence of interventions received: 1. High Performers; Continued IAU & Monitoring; 2. Improved Performers; Continued A/F; 3. Improved Performers; A/F then step-down to IAU; 4. Low Performers; Continued A/F; 5. Low Performers; A/F + EF; 6. Low Performers; Continued IAU & Monitoring. **b.** Exploratory Aims: We will employ a mixed-methods approach to evaluate additional implementation and clinical outcomes addressed in the exploratory aims.

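### The SAP tests the primary aim and aim 2b with an unadjusted spline contrast in place of the protocol's baseline- and strata-adjusted regression, and does not say why

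*SAP*

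**What the plan says.** **Protocol, C7.b (Primary Aim).** Change in each primary outcome, from the last baseline month to month 10 of Phase I, is regressed on group, "the baseline outcome value, the stratification variables of facility complexity (high, medium, low) and baseline performance level", and geographic region.

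**Protocol, C7.c (secondary aim 1, the SAP's aim 2b).** Change over Phase II is modelled on group, "the baseline outcome value, the stratification variables and geographic region (if sample sizes allow for control of this variable"). Only region is conditional on numbers.

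**Protocol, C7.c, end.** A B-spline mixed model comes after the tests of the aims and has another purpose: "Lastly, we will use a data driven approach to characterize each of the four EPRP outcomes over time". It covers groups 1 to 6, has a random intercept and slope, and lists no baseline, strata or region terms.

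**Protocol, C5.b.** "R1 will be stratified by facility complexity level (i.e., high, medium and low) and level of performance (i.e., low or moderate) at baseline". The second randomization of non-responders (R2) is stratified on the same two factors.

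**SAP, Primary Aim.** The test is a contrast, fitted November minus fitted February 2021, from a model with a random site intercept: "Each outcome was then modeled as a function of group, the B-spline transformations, and group by B-spline transformation interactions". The reason offered is "We chose to estimate these trajectories using natural cubic B-spline transformations on time to allow for smoothly changing trajectories", as against a parametric form such as polynomials.

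**SAP, Secondary Aim 2b.** Adherence is modelled "as a function of group (Continued AF and Added EF), B-spline transformations on time, and group by B-spline transformation interactions", with the contrast running from January 2022 to July 2023.

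**The concern.** The protocol names a test and its covariates. The SAP uses another test without those covariates, and its one stated reason answers a different question: how to shape the time curve, not why the adjusted regression was replaced.

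Three things are at stake. The baseline value and the strata are already held and could sharpen the primary comparison. A chance difference between arms at baseline is left unadjusted: January 2021 enters the SAP model as a response, but the group main effect is free, so the contrast does not condition on it. And a reader cannot tell what the prespecified analysis would have shown. That matters more because the SAP is written in the past tense and places its knots where change points were visible in descriptive plots.

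**Working it through.** **1. The plan's own power figures.** Protocol C7.a uses a two-sample t-test with SD 0.10 and 80% power. Solving the noncentral t for the detectable difference:

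| Comparison | n per arm | alpha | Recomputed | Stated |
|---|---|---|---|---|
| Primary, N=112 | 56/56 | 0.025 | 0.0589 | 0.059 |
| Primary, N=126 | 63/63 | 0.025 | 0.0555 | 0.055 |
| Adding EF, N=56 | 28/28 | 0.05 | 0.0762 | 0.076 |
| Adding EF, N=63 | 31/32 | 0.05 | 0.0717 | 0.072 |

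These reproduce. They assume no covariates, so leaving covariates out does not undercut them. At the SAP's 67 vs 66 the same formula gives 0.054. At 38 vs 17 it gives 0.083, which reflects the uneven split (28 vs 27 would give 0.077), not the missing adjustment.

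**2. Chance imbalance.** For a simple change score, a baseline difference D shifts the unadjusted contrast by (1 − rho) × D, where rho is the baseline to follow-up correlation. The documents give no rho. With D = 0.05, an assumed rho of 0.9 gives 0.005 and an assumed rho of 0.3 gives 0.035. This only approximates the spline contrast, which pools months.

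**3. Precision.** Take a natural cubic spline over months 1 to 39 with knots at 11, 13, 23 and 27 (5 df). With complete data, the SAP contrast is the arm difference in c′y, where y is a site's 39 months and c is the least-squares row for fitted month 11 minus that for month 2. Covariates entered as main effects only leave c′y unchanged; they must be crossed with the spline terms.

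The variances are assumptions. With the month-1 SD set to 1, 3 × 4 × 5 = 60 structures were simulated:
- random-intercept share 0.3, 0.5 or 0.7;
- AR(1) share/correlation none, 0.1/0.7, 0.2/0.9 or 0.25/0.5;
- slope SD per 10 months (correlation with intercept) 0, 0.3 (0), 0.5 (−0.5), 0.8 (0) or 0.8 (−0.5).

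Strata were complexity at 61/17/22% and a median split on the mean of two outcomes correlated 0.5 (assumed). SD of the adjusted spline contrast divided by that of the SAP contrast:
- Primary aim, n = 133, strata only: 0.996 to 1.001.
- Primary aim, January value plus strata: 0.897 to 1.001, median 0.942. The gain is about 0% to 10% and comes from the baseline value.
- Aim 2b, n = 55 at 38:17, November 2021 value plus strata: 0.887 to 1.019, median 1.004. No gain should be expected.

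Missing months and the selection of R2 sites below the benchmark are not modelled.

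**4. Do the two analyses estimate the same thing?** Let a true effect of 1.0 be reached by the final month and then kept. Change from the last pre-phase month targets 1.00. The SAP contrast starts in the first month of each phase and smooths across the early months. Applying c to each effect curve:

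| How the effect builds | Primary (Feb–Nov 2021) | 2b (Jan 2022–Jul 2023) |
|---|---|---|
| Linear over the phase | 0.84 | 0.88 |
| Over 3 months | 0.69 | 0.49 |
| At once | 0.41 | 0.36 |

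The targets differ.

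**5. Intervals from the random-intercept model.** The true variance of the contrast is c′Vc for covariance matrix V. The random-intercept model uses the pooled within-site variance times c′c. Over the same 60 structures, ignoring stratification, model SE divided by true SD is 0.67 to 1.00 for the primary aim (median 0.85; a nominal 95% interval then covers about 90%). For aim 2b it is 0.32 to 1.00 (median 0.42; about 59%).

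**The case against.** The strongest reply is that the protocol itself planned an unadjusted spline mixed model, that randomization makes adjustment unnecessary, and that a model of all 39 months should beat a regression on two single months.

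The first part stands in a limited sense. The model form was not invented for the SAP. But the protocol used it to describe trajectories, and the SAP made it the hypothesis test and dropped the random slope.

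The second part stands as regards bias. A reader might infer that the unadjusted contrast is biased or that the trial is now underpowered. The documents support neither: sites were randomized, and the power figures never relied on covariates.

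The third part does not stand as a ranking. In the same simulations the two-month regression had an SD 1.113 to 1.931 times that of the primary spline contrast (median 1.374), but the two measure different quantities. For a full effect of 1.0, the regression's signal-to-noise relative to the spline's SD is 1/1.374 = 0.73. The spline's is 0.84 for a linear build, 0.69 for a 3-month build and 0.41 for an immediate effect. Which does better depends on how fast the effect appears, and the documents do not say. Part of the spline's apparent advantage may also be intervals that are too narrow.

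It is also fair that little precision is at stake, and none should be expected in 2b.

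**Conclusion.** The departure is plain from the text: the protocol's adjusted regression was replaced as the test for both aims, its covariates are absent, and no reason is given for either change. This is a point to correct at low cost; it does not invalidate the comparison.

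The loss is modest. For the primary aim it is about 0% to 10% of the SD, resting wholly on assumed variance structures, because the documents give no within-site correlation. Protection against chance baseline imbalance and traceability to the planned test are also lost. The case for reporting the planned regression holds even if the precision gain is zero.

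A reader might infer that the model was chosen for a favourable result. The documents show that knots were set from descriptive plots. They do not show when, or on what grounds, the regression was set aside.

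**What to change.** 1. **Report the protocol's regression beside the spline contrast, and state why it was replaced.** Apply it to eCSSRS1 and eCSRE1.
   - Primary aim: change from January to November 2021 on group, baseline value, complexity, performance level and region. That is 1 + 1 + 1 + 2 + 1 + 4 = 10 parameters, leaving 133 − 10 = 123 df (t multiplier at alpha 0.025: 2.269, against 2.267 unadjusted).
   - Aim 2b: change from November 2021, before R2, to July 2023. Include region only if numbers allow; without it there are 6 parameters and 55 − 6 = 49 df (2.010 against 2.006 at alpha 0.05).
   - With the baseline value in the model, using change or the final value gives the same group coefficient.
2. **State that the two analyses have different targets.** Do not rank them by SD or read a difference as disagreement. Show the spline contrast over the same windows as well (January to November 2021; November 2021 to July 2023). This brings them closer, though smoothing still attenuates a fast effect.
3. **Optional, labelled as chosen after analysis.** For the primary aim, cross the January 2021 value, complexity and performance level with the spline terms (4 main effects and 4 × 5 = 20 interactions). Use the protocol's random slope or site-robust standard errors.

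Leave out aim 2a: 6 vs 6 sites cannot support the adjustment.

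The cost is SAP wording, four short regressions, the re-windowed contrasts and, if wanted, two adjusted spline fits, with no new data. The downside is wider intervals from the regressions. Their form was prespecified, though not for these outcomes, and the SAP should say so.
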